The purpose of this research is to promote caregiver health and well-being by intervening with caregivers of people with dementia. The long-term goal of this research is to promote public health and alleviate suffering among a growing population of ADRD caregivers and PWD. To this end, we will evaluate the impact of CommunityRx-Caregiver (CRx-C), a scalable information technology-based intervention, developed with the target community, to address unmet community resource needs.

The over-arching aims of the program of research are:

Aim 1: Among caregivers with unmet HRSNs, evaluate the effects of CRx-C versus usual care on caregiver self-efficacy (primary outcome) and secondary outcomes: psychosocial (unmet needs, social isolation, well-being, burden, depression, stress), behavioral (community resource use), health and healthcare utilization.

Aim 2: Among all caregivers (those with and without unmet HRSNs), evaluate acceptability of the intervention as well as the effects of CRx-C versus usual care on the health care experience, including satisfaction with care (primary outcome), experiences of stigma during clinical care and likelihood of sharing community resource information with others.

Aim 3: Among a purposeful sample of caregivers, assess: (a) experiences with CRx-D; (b) the role of stigma in disclosing needs and accessing resources; and (c) experiences sharing resource information with others.

Findings will yield an understanding of how best to leverage ADRD caregivers' or care recipients' healthcare visits to identify, support and improve outcomes for caregivers, including psychosocial characteristics, behaviors, health and healthcare. Results will inform whether and how CRx-C should be implemented in practice and explore how best to sensitively and effectively intervene to support all ADRD caregivers.

The pretest study aims to identify optimal processes for administering the planned intervention remotely or in-person and to optimize the efficiency and flow of baseline and follow-up survey administration and interval communications with participants. Findings from this pretest will be presented to the CommunityRx-Caregiver Advisory Board which consists of a diverse sub-group of ADRD caregivers and other community stakeholders. Their input and feedback will be used to inform the larger randomized trial.

C. Methodology

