The 344 caregivers enrolled in the RCT for a 12-month follow-up will complete an intervieweradministered baseline survey (by phone, video or online) and phone- or web-based follow-up surveys at 7 days, one month, 3 months, and 12 months after the index visit. The 50 additional male caregivers enrolled in the RCT for a 3-month follow-up will complete an interviewer-administered baseline survey (by phone, video or online) and phone- or web-based follow-up surveys at 7 days, one month, and 3 months after the index visit. Surveys will elicit self-reported data in the following domains: caregiver status, caregiver sociodemographic characteristics (e.g., age, race/ethnicity, sex and gender), caregiver-reported care recipient demographics (e.g. age, race/ethnicity), employment, household composition, income and insurance status, stage of dementia of the care recipient; psychosocial characteristics (e.g., caregiver self-efficacy, unmet health-related social and caregiving needs, burden, depression, stress and well-being); behaviors (e.g., use of resources, use of the Community Resource Finder, resource information sharing, activation of the Community Resource Specialist); health and healthcare use (e.g., physical health and healthrelated quality of life and healthcare utilization); and healthcare experience (e.g., satisfaction with care, stigma). Caregivers will be asked a limited number of questions as proxy for the care recipient to assess: well-being, community resource needs and use, health and healthcare utilization.

If needed to supplement healthcare utilization data, we will obtain health insurance claims for the participant. The informed consent/assent process will inform study participants of the rationale for accessing these data and request participants' permission to do so.

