**Health and Healthcare Outcomes** Caregiver physical health will be assessed using the Medical Outcomes Study SF-12 and EMR data. Physical health of the PWD will be assessed by proxy using a single item global measure of physical health. Healthcare utilization will be assessed using the DEXCOM, a self-report tool developed by Co-PI [name] et al and used in CRx-2. We will explore outcomes such as days to, number and duration of ER/hospital visits, and patterns of 911 and ambulance use to test the hypothesis that supporting caregivers with community resources is associated with less need for emergency healthcare services.

**Analysis and Sample Size Justification:** To determine the impact of CRx-D on the highest risk group, Aim 1 analyses will focus on 172 caregivers with at least 1 HRSN. Descriptive statistics will be used to summarize, overall and by study arm, sociodemographic characteristics and primary

and secondary outcomes at each measured time point. The mean, standard deviation, median, and inter-quartile range will be generated for continuous variables; frequency counts and percentages will be generated for categorical variables.

The main analyses will follow the principle of intent-to-treat, and include all 172 ADRD caregivers with at least 1 unmet HRSN in the study arm to which they were allocated. We aim to minimize missing data by employing interviewer-administered surveys and communicating to participants the protections of a certificate of confidentiality. Using these strategies, item non-response ranged from 0-3% in the CRx-2 trial. To avoid potential bias due to missing data, analyses will be conducted using multiple imputation with the chained equations method or inverse probability weighting to account for dropout and/or item non-response. In addition, characteristics of caregivers who complete each follow-up survey will be compared to caregivers who do not.

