## Analysis Plan

To determine the impact of CRx-D on the highest risk group, Aim 1 analyses will focus on 172 caregivers with at least 1 HRSN. Descriptive statistics will be used to summarize, overall and by study arm, sociodemographic characteristics and primary and secondary outcomes at each measured time point. The mean, standard deviation, median, and inter-quartile range will be generated for continuous variables; frequency counts and percentages will be generated for categorical variables.

The main analyses will follow the principle of intent-to-treat, and include all 172 ADRD caregivers with at least 1 unmet HRSN in the study arm to which they were allocated.

To fully leverage the longitudinal data, generalized linear mixed-effects models (GLMM) will be fit with particular interest in the time (7, 30, 90 days and 12 months post-enrollment) by study arm interaction; baseline values will be included as a covariate. Based on this model, appropriate contrasts to test the intervention effect at specific time points (e.g., 12 months) will be constructed. These contrasts will permit examination of early versus late intervention effects, valuable information for future iterations of this and other ADRD caregiver self- and family management interventions. GLMM can be used for continuous (e.g., mean caregiver self-efficacy for providing care score, patient satisfaction score, stigma score), ordinal (e.g., physical health of PWD by proxy) or binary (e.g., resource use, resource sharing) outcomes. Models will include covariates moderately associated with the outcome to remove differences attributable to baseline covariates and increase precision of the estimate of the treatment affect. Latent growth curve modeling is a viable alternative to GLMM and will be explored when sufficient variability in the distributions of patterns of outcomes by time points exist (e.g., with the binary outcomes there will be a limited number of potential patterns).

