We will also use survival analysis methods and methods for analyzing count data (e.g., Poisson or negative binomial regression) to explore acute and emergency healthcare utilization. For example, time from enrollment to first home EMS or ER visit will be calculated for each subject and those who never have one of these events will be censored at the end of study follow-up. Stratified Cox proportional hazards regression models will be fit with intervention group as the independent variable and clinical enrollment site as a stratification factor, due to the potential for different underlying rates based on clinical site. The proportional hazards assumption will be checked using log-log plots of survival and Schoenfeld residuals.

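### The exploratory Cox model for time to first EMS or ER visit names no baseline utilization term, which gives up some power if prior acute-care use is prognostic

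*SAP*

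**What the plan says.** The Cox model appears twice in the same words: in the Overall Statistical Analysis Plan (Aim 1, Analysis and Sample Size Justification) and in the Aim 1 Statistical Analysis Plan (Analysis Plan). Both say: "Stratified Cox proportional hazards regression models will be fit with intervention group as the independent variable and clinical enrollment site as a stratification factor". The endpoint is introduced as an illustration: "For example, time from enrollment to first home EMS or ER visit will be calculated for each subject". The purpose of the survival and count methods is "to explore acute and emergency healthcare utilization", and the Overall plan (Health and Healthcare Outcomes) likewise says "We will explore outcomes such as days to, number and duration of ER/hospital visits". No terms are listed for the count models.

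The final protocol (B. Purpose, Aim 1) ends its list of secondary outcomes with "behavioral (community resource use), health and healthcare utilization", so utilization is secondary as a domain. In C. Methodology the protocol names the baseline and follow-up surveys together and then lists their domains, including "quality of life and healthcare utilization". Section F adds the electronic medical record as a source for utilization.

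For the mixed models, the Aim 1 Analysis Plan says that "baseline values will be included as a covariate". A later sentence in that paragraph says models will carry covariates with a moderate association with the outcome. Neither statement is repeated for the survival or count models.

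**The concern.** Elsewhere the plan uses each caregiver's starting point. The mixed models adjust for the baseline value, and the transition models condition on the previous state. The Cox model is stratified by site because underlying rates may differ between sites, so the plan accepts that unequal underlying risk should be handled. A caregiver's own earlier ER, hospital or EMS use is plausibly a more direct marker of that risk, yet it is not named.

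Randomization is stratified only by HRSN status (0 or at least 1). All 172 caregivers in the Aim 1 analysis set have at least one need, so within that set the design does nothing to balance prior acute-care use.

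At stake is the chance of detecting a real reduction in emergency care, which the Overall plan states as a hypothesis, in a sample that was not sized for it.

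**Working it through.** **The plan's own figure.** The only Aim 1 sample-size statement concerns self-efficacy: 86 per arm to detect 0.43 points, SD 1, alpha 0.05, power 0.8. Normal approximation: n = 2 × (1.960 + 0.842)² / 0.43² = 84.9, so 85 per arm. The t-test version gives 85.9, so 86. The figure reproduces as two-sided. It says nothing about the Cox analysis, for which no event count, hazard ratio (HR) or power is given.

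**Starting power without a covariate.** Schoenfeld: power = Φ(√(d/4) × |ln HR| − 1.96), where d is the number of events. With 172 caregivers, an assumed 40% of them having an event, and HR 0.6: d = 68.8, √17.2 × 0.511 − 1.96 = 0.158, power 56%. At 30%, 50% and 60% the power is 45%, 66% and 74%. The HR detectable with 80% power runs from 0.46 (30% events) to 0.58 (60% events).

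**Simulation.** Assumed: 86 per arm, conditional treatment HR 0.6, 40% of caregivers with prior use, exponential times censored at 12 months, two-sided 5% Wald test, 2,000 runs per row. Site strata and dropout were not simulated.

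| Control events | Prior-use HR | Arm only | Adjusted | Gain (points) |
|---|---|---|---|---|
| 40% | 1.0 | 47.6% | 47.6% | 0.0 |
| 40% | 1.5 | 47.3% | 47.6% | 0.3 |
| 40% | 2 | 44.3% | 45.8% | 1.5 |
| 40% | 3 | 43.2% | 47.9% | 4.7 |
| 40% | 5 | 39.0% | 47.9% | 8.9 |
| 60% | 1.0 | 66.3% | 66.0% | −0.3 |
| 60% | 1.5 | 65.3% | 66.8% | 1.5 |
| 60% | 2 | 63.6% | 66.5% | 2.9 |
| 60% | 3 | 56.4% | 65.5% | 9.1 |
| 60% | 5 | 48.2% | 67.8% | 19.6 |

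Check on the first row: the control hazard is −ln 0.6 = 0.511, so the treated event probability is 1 − exp(−0.6 × 0.511) = 0.264. Events are 86 × 0.40 + 86 × 0.264 = 57.1. Schoenfeld power is Φ(√14.3 × 0.511 − 1.96) = 49%, close to the simulated 47.6%. The Monte Carlo standard error of a single power figure is about √(0.45 × 0.55 / 2000) = 1.1 points.

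A separate simulation (3,000 runs, control rate set nominally from the mean hazard) gave these figures at 40% and 60% control events:

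- Prior-use HR 2: 45.0% to 47.5%, and 63.0% to 65.9%.
- Prior-use HR 3: 40.6% to 44.3%, and 54.0% to 61.8%.
- Prior-use HR 4: 37.9% to 43.7%, and 48.0% to 62.2%.
- All 344 caregivers, treatment HR 0.7, prior-use HR 3: 42.6% to 48.7%, and 55.9% to 64.4%.

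**Where the gain comes from.** Take 40% control events and prior-use HR 3. The mean arm-only HR is 0.617 with standard error 0.271; the adjusted HR is 0.596 with standard error 0.273. Arm only: |ln 0.617| / 0.271 = 1.78, power Φ(1.78 − 1.96) = 43%. Adjusted: |ln 0.596| / 0.273 = 1.90, power Φ(1.90 − 1.96) = 47%. The standard error does not shrink. The arm-only HR lies nearer 1 because the hazard ratio is non-collapsible.

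**The case against.** The strongest case against is that this is a preference about an exploratory example. Its parts stand to different degrees.

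- **Status.** A reader might infer that a prespecified secondary endpoint loses power. The documents do not support that: only the utilization domain is secondary, time to first visit is exploratory, and no power is claimed for it. This stands.
- **The covariate rule.** A reader might infer that the plan restricts these models to arm. It does not say so. The covariate sentence speaks of models in general, and the count models list no terms at all, so their silence may be brevity. However, the sentence sits in the mixed-model paragraph, and the survival paragraph gives its own specification. What remains is that its reach is unstated.
- **Availability.** Baseline collection is implied by the joint list of survey domains, not itemized, and no look-back period is given. The medical record may not cover caregivers who are not patients, whom the protocol also recruits. This stands as a condition on the fix.
- **Validity.** A reader might infer that the arm-only result is biased, or that chance imbalance invalidates it. Neither follows. The randomized comparison is valid, its type I error already allows for chance imbalance, and the arm-only HR targets a marginal effect, not a conditional one.
- **Size.** All inputs are assumed, and the site strata left out of the simulations may absorb some prognostic variation. This stands.

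None of this shows that the arm-only model does as well when prior use is prognostic, or that adjusting does harm. With no prognostic effect, the simulated change was 0.0 and −0.3 points, within simulation error.

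**Conclusion.** The point holds in a narrow form, as a minor improvement. The survival and count specifications name no baseline utilization term, and the plan leaves open whether its covariate rule reaches them. Across the two simulations the gain from adjusting is about 0 to 3 power points for a prior-use HR up to 2 and about 4 to 9 points at 3. Larger gains (about 6 to 14 points at 4, about 9 to 20 at 5) need a predictor stronger than anything the documents establish. The event rates, the treatment HR, the 40% prevalence and the prognostic strength are all assumptions.

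A reader might also infer that the adjustment is free. It is cheap, but it changes the quantity estimated. No primary conclusion is affected.

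**What to change.** First confirm that ER, hospital and EMS use is recorded at baseline, and over what look-back period. Then amend the survival and count paragraph in both places where it appears:

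- Include the caregiver's baseline acute-care use (survey, supplemented by the medical record where available) as a covariate in the Cox and the Poisson or negative binomial models.
- Keep site as the stratum in the Cox model.
- Impute missing baseline values under the existing Handling of Missing Data rule.
- Report the arm-only model as a sensitivity analysis.

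The SAP already refers to data analysis in the past tense. If these models have been run, report the adjusted model as a labelled additional analysis.

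Cost: a sentence or two of SAP wording and one covariate. The hazard ratio becomes conditional on prior use and should be described that way. A few baseline values will need imputing; item non-response in the earlier CRx-2 trial was 0–3%.

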### Handling of Missing Data

We aim to minimize missing data by employing interviewer-administered surveys and communicating to participants the protections of a Certificate of Confidentiality. Using these strategies, item non-response ranged from 0-3% in the CRx-2 trial. To avoid potential bias due to missing data, analyses will be conducted using multiple imputation with the chained equations method or inverse probability weighting to account for dropout and/or item non-response. In addition, characteristics of caregivers who complete each follow-up survey will be compared to caregivers who do not. We will follow all caregivers through 12 months even if they no longer care for the PWD.

# Additional Information, Clarification, Changes *Aim 1*:

For each Aim, there is a single primary outcome, and no multiplicity adjustment will be made to the analyses of the secondary outcomes. Analyses will also be performed in the overall group (irrespective of baseline HRSNs) and among those without baseline HRSNs.

These analyses aim to fill a gap in knowledge about the effectiveness of a universal intervention approach. The treatment group by baseline HRSN status interaction will also be tested.

Since a majority of participants were female and African American or Black, formal interaction testing was not performed.

Models will also be fit with the intervention group separated into two subgroups (those with at least 1 adhoc HealtheRx vs not).

### Introduction

The purpose of Aim 2 is to test the hypothesis that a universal approach to delivery of the CRx-D intervention is acceptable to caregivers and does not diminish caregiver satisfaction with care [primary outcome] or cause caregiver harm relative to usual care.

#### **Measures Used**

#### Satisfaction with Care

Satisfaction will be assessed 7 days post-discharge from the caregiver's ambulatory visit using the Patient Satisfaction Questionnaire 18-item short form (PSQ-18). The PSQ-18 is widely used in research and shows internal consistency with the PSQ long form, an 80-item survey developed in 1976. The 18 items are grouped into 7 domains; each domain is scored separately (there is no overall score). The general satisfaction sub-scale of the PSQ (2/18 questions) is the most relevant PSQ domain for our study.

